| Study Objectives | 
Primary Study Objective:
 
 To observe the Clinical Benefit Rate (CBR) and Progression Free survival Rate (PFR) of apatinib combined with SHR-1210 for patients with advanced osteosarcoma. 
Secondary Study Objectives:
 
 To compare the efficacy of apatinib combined with SHR-1210 for patients with advanced osteosarcoma, through evaluations of overall survival (OS), objective response rate (ORR), disease control rate (DCR), and duration of response (DoR); 
Exploratory Study Objectives:
 
 To evaluate the quality of life (QoL) of patients with advanced osteosarcoma who receive SHR-1210 combined with apatinib; To explore the correlation between biomarkers and the efficacy of combined therapeutic regimen; |
| Study Endpoints | 
Primary Study Endpoints:
 
 6 months PFR; 
Secondary Study Endpoints:
 
Efficacy:
 
 OS, PFS, ORR, DCR and DoR based on iRECIST v1.1; 
Safety:
 
 Incidence and severity of adverse events (AEs) and serious adverse events (SAEs) judged in accordance with NCI-CTCAE v4.03; vital signs, ECG and abnormal laboratory examinations. 
Exploratory Study Endpoints:
 
 Average score and its change in the score from baseline in all the subscales of EORTC QLQ-C30; |

| | |
|--------------------------------|--|
| Study Subjects | Patients with incurable, locally advanced or metastatic osteosarcoma |
| Study Design | 
This is a Single-arm, Open label, Prospective, Single-center Clinical Trial to evaluate the efficacy and safety of PD-1 antibody SHR-1210 plus Apatinib Mesylate Tablets in patients with advanced Osteosarcoma.
 
Primary efficacy endpoint is 6 months PFR based on RECIST v1.1, and approximately 38 subjects who could be evaluated will be enrolled.
 
Subjects will receive study treatment after being informed of all pertinent aspects of the study, signing the informed consent form and passing the screening for eligibility. SHR-1210, 200 mg, via intravenous infusion, once every two weeks (Q2W) + Apatinib Mesylate Tablets 500 mg, p.o., once per day (QD), continuously, 4 weeks (28 days) per cycle of therapy, until meeting the criteria for study treatment termination specified in the protocol. Subjects will continue to receive safety and survival follow-up after end of treatment. Subjects who discontinue treatment for reasons other than progression of disease will continue to receive regular radiological evaluation follow-up after end of treatment.
 
Subjects will have safety visits on D1 of every 2 cycles; Radiological examination will be performed once every 8 weeks to evaluate efficacy until progression of disease is determined (non-pseudoprogression), start of a new anti-tumor therapy, withdrawal of informed consent, death, or termination of the study by the sponsor, whichever comes first.
 |
| Study Drug | 
SHR-1210 for Injection (Generic Name: Camrelizumab for Injection) (Manufacturer: Suzhou Suncadia Biopharmaceuticals Co., Ltd.)
 
Apatinib Mesylate Tablets (Manufacturer: Jiangsu Hengrui Medicine Co., Ltd.)
 |
| Route of Administration | 
SHR-1210 200 mg will be infused intravenously (premedication is not required). Each infusion will be administered over 30 min (no less than 20 min, no more than 60 min), once every two weeks;
 
Apatinib Mesylate Tablets 500 mg is administered orally after meals within 30 min, once per day, continuously.
 |
| Inclusion Criteria | 
Subjects can be enrolled in this study only when they meet all the inclusion criteria:
 
 1. Provided informed consent and sign the informed consent form; 2. ≥ 11 years old, male and female; |

3. Histopathologically or cytologically confirmed Advanced Osteosarcoma; (Local tumors and solitary pulmonary lesions must be confirmed by pathological diagnosis. Multiple pulmonary metastases need no pathological examination.)
4. Failed to receive chemotherapy for osteosarcoma (including HD-MTX, anthracyclines, DDP and IFO) are defined as those who progress within 6 months after adjuvant chemotherapy and chemotherapy for advanced osteosarcoma, and those who progress over 6 months require the consent of the subject or his legal representative.;
5. Have at least one measurable lesion (in accordance with RECIST v1.1, major diameter ≥ 10 mm of the measurable lesion in spiral CT scan or short diameter of swollen lymph node ≥ 15 mm; the lesion with previous local therapy can be used as target lesion after the progression is confirmed in accordance with RECIST v1.1);
6. For subjects with progression after local regional therapy, the local regional therapy (including but not limited to surgery, radiotherapy, hepatic artery embolization, TACE, hepatic arterial infusion, radiofrequency ablation, cryoablation or percutaneous ethanol injection) must has been completed at least 4 weeks prior to baseline radiological scanning, and any toxicity (except alopecia) induced by local regional therapy must have resolved to \leq Grade 1 in accordance with national cancer institute – common terminology criteria for adverse event version 4.03 (NCI-CTCAE v4.03);
7. ECOG-PS score 0-1;
8. With a life expectancy of ≥ 12 weeks;
9. The body surface area is over 1.2m^2 ;
10. Have the required screening laboratory values including the following parameters (within 7 days prior to the start of study treatment):
 - (1) Hematology: (except for hemoglobin, no blood transfusion or use of granulocyte colony-stimulating factor [G-CSF] or use of drugs for correction within 14 days prior to screening);
 - Absolute neutrophil count $\geq 0.75 \times 10^9/\text{L}$;
 - Platelet count $\geq 75 \times 10^9/\text{L}$;
 - Hemoglobin ≥ 80 g/L;
 - (2) Blood biochemistry: (no infusion of albumin within 14 days):

| | |
|----------------------------------|--|
| | 
 • Serum albumin ≥ 25 g/L; • Serum total bilirubin $\leq 1 \times$ upper limit of normal (ULN); • Alanine aminotransferase (ALT), aspartate aminotransferase (AST) and alkaline phosphatase (AKP) $\leq 2.5 \times$ULN; • Serum creatinine (Cr) $\leq 1.5 \times$ULN or Cr clearance > 50 mL/min (Cockcroft-Gault formula as below) Man: Cr clearance = $((140 - \text{age}) \times \text{weight}) / (72 \times \text{serum Cr})$ Woman: Cr clearance = $((140 - \text{age}) \times \text{weight}) / (72 \times \text{serum Cr}) \times 0.85$ Weight unit: kg; serum Cr unit: mg/mL; 
11. Women of childbearing potential: must agree on abstinence (avoid heterosexual intercourse) or use of contraception methods with annual contraceptive failure rate of $< 1\%$ following the signature of informed consent form until at least 120 days after the last dose of study drug. The serum human chorionic gonadotropin (HCG) test must be negative within 7 days prior to enrollment in the study; and the subjects must not be in lactating period.
 
If the female subject has menses, has not reached postmenopausal state (absence of menses for \geq consecutive 12 months, with no other reason found except menopause) and has not received sterilization operation (e.g., hysterectomy, bilateral tubal ligation or bilateral ovariectomy), she would be considered to have childbearing potential.
 |
| 
Exclusion Criteria
 | 
Subjects who meet any one of the following criteria must not be enrolled in this study:
 
 1. Other active malignant tumor except advanced osteosarcoma within 5 years or simultaneously. Cured localized tumor, for example, basal cell carcinoma of skin, squamous cell carcinoma of skin, superficial bladder cancer, carcinoma in situ of prostate, carcinoma in situs of cervix, breast cancer in situ may be enrolled; 2. History of gastrointestinal hemorrhage within 6 months prior to the start of study treatment or clear tendency of gastrointestinal hemorrhage, for example, esophageal and fundal varices with hemorrhagic risk, locally active peptic ulcer, persistent fecal occult blood (+) (the fecal occult blood test can be repeated if it is positive at baseline, and gastroduodenoscopy |

| | |
|--|--|
| | 
[EGD] would be needed if it is still positive in repeated test; the patient can not be enrolled if the EGD shows esophageal and fundal varices with hemorrhagic risk);
 
 3. Abdominal fistula, gastrointestinal perforation or intraperitoneal abscess within 6 months prior to the start of study treatment; 4. Known genetic or acquired hemorrhage (e.g., coagulation dysfunction) or thrombotic tendency, for example, patient with hemophilia; current or recent (within 10 days prior to the start of study treatment) use of full-dose of oral or intravenous anticoagulant or thrombolytic drug for the purpose of treatment (preventive use of low-dose aspirin or low molecular weight heparin is allowed); 5. Current or recent (within 10 days prior to the start of study treatment) use of aspirin (> 325 mg/day) or dipyridamole, ticlopidine, clopidogrel and cilostazol; 6. Thrombosis or thromboembolic event within 6 months prior to the start of study treatment, for example, cerebrovascular accident (including transient ischemic attack, cerebral hemorrhage, cerebral infarction), pulmonary embolism; 7. Cardiac clinical symptom or disease that is not well controlled, for example, (1) > Grade II cardiac insufficiency in accordance with New York Heart Association (NYHA) criteria or color Doppler echocardiography: LVEF (left ventricular ejection fraction) <50%; (2) unstable angina pectoris; (3) myocardial infarction within one year prior to the start of study treatment; (4) clinically significant supraventricular or ventricular arrhythmia requiring treatment or intervention; (5) QTc > 450 ms (males) or QTc > 470ms (females) (QTc interval is calculated by Fridericia formula; In case QTc is abnormal, it can be detected for three times at an interval of 2 minutes and the average will be taken); 8. Hypertension that can not be well controlled through antihypertensive drugs (systolic blood pressure \geq140 mmHg or diastolic blood pressure \geq90 mmHg) (based on the average of BP readings acquired from \geq2 measurements), allowing to reach the above parameters by the use of antihypertensive therapy; previous hypertensive crisis or hypertensive encephalopathy; 9. Major vascular disease within 6 months prior to the start of study treatment (for example, aortic aneurysm |
|--|--|

- requiring surgical repair or peripheral arterial thrombosis in recent days);
10. Serious, uncured or splitting wound and active ulcer or untreated bone fracture;
 11. Major surgical therapy within 4 weeks prior to the start of study treatment (except diagnosis), or expected major surgery during the study;
 12. Inability or unwilling to swallow tablets, malabsorption syndrome or any condition affecting gastrointestinal absorption;
 13. Intestinal obstruction and/or clinical signs or symptoms of gastrointestinal obstruction within 6 months prior to the start of study treatment, including incomplete obstruction that is related with the original disease or needs routine parenteral hydration, parenteral nutrition or tube feeding;
 - If the subject has signs/symptoms of incomplete obstruction/ obstructive syndrome/intestinal obstruction at the initial diagnosis receives clear (surgical) therapy to resolve symptoms, the subject may be enrolled;
 14. Evidence on intraperitoneal pneumatosis that can not be explained by puncture or recent surgery;
 15. Previous or current presence of metastasis to central nervous system;
 16. Previous or present history of pulmonary fibrosis, organising pneumonia (e.g., obliterative bronchiolitis), interstitial pneumonia, pneumoconiosis, drug related pneumonitis, idiopathic pneumonia, or allowable previous radiation pneumonitis in the radiation area (fibrosis) for subjects with evidence on active pneumonia or serious pulmonary function impairment on thoracic computed tomography (CT) in screening period that may interfere with the detection and treatment of suspected drug related pulmonary toxicity; active tuberculosis;
 17. Any active autoimmune disease or history of autoimmune disease and expected recurrence (including but not limited to autoimmune hepatitis, interstitial pneumonia, uveitis, enteritis, hypophysitis, vasculitis, nephritis, hyperthyroidism, hypothyroidism [subjects that can be controlled with hormone replacement therapy only can be enrolled]); subjects with skin diseases that does no need systemic treatment, for example, leukoderma, psoriasis, alopecia, those with controlled type I diabetes by insulin or those with asthma that has been completely

- resolved in childhood and with no need of any intervention can be enrolled; while subjects with asthma who need bronchodilator for medical intervention can not be enrolled;
18. Current use of immunosuppressive medication, or systemic corticosteroid therapy to achieve the objective of immunosuppression (Prednisone at the dose of >10mg/day or equivalent), and continuous use within two weeks prior signing informed consent form;
 19. Use of strong CYP3A4/CYP2C19 inducers, including rifampicin (and its analogues) and St. John's Wort, or strong CYP3A4/CYP2C19 inhibitors within two weeks prior to the signature of informed consent form;
 20. Known history of serious allergy to any monoclonal antibody or targeted anti-angiogenic drug;
 21. Severe infection within 4 weeks prior to the start of study treatment, including but not limited to hospitalization for infection, bacteremia or complications of severe pneumonia; oral or intravenous therapeutic antibiotics within two weeks prior to the start of study treatment (for example, subjects who are given with preventive antibiotics for prevention of urinary tract infection or exacerbation of chronic obstructive pulmonary disease are eligible for participation in the study);
 22. Congenital or acquired immunodeficiency (e.g., HIV infection);
 23. Combined hepatitis B and hepatitis C co-infection;
 24. Previous treatment with other PD-1 antibody or other immunotherapy against PD-1/PD-L1, or previous use of other small molecules of anti-angiogenesis TKI drugs, such as pazopanib, sorafenib;
 25. Palliative radiotherapy for non-target lesions to control symptoms is allowed, but it must be completed at least 2 weeks prior to the start of study treatment, and the adverse event induced by radiotherapy must have resolved/improved to \leq CTCAE Grade 1;
 26. Treatment of other investigational product(s) within 28 days prior to the start of study treatment;
 27. Other factors that may affect the study results or lead to forced termination of the study early as judged by investigators, such as alcoholism, drug abuse, other serious diseases (including mental disorders) requiring concomitant therapy, with serious laboratory

| | |
|--|--|
| | examination abnormality, with family or social factors, that may affect subject's safety. |
| Criteria For Termination of Study Treatment | 
Termination of study treatment does not represent withdrawal from the study. Subjects who terminate the study treatment must continue to complete the remaining study visits as required in the protocol. Subjects must terminate study treatment when any of the following conditions occurs:
 
 • Subject requests termination of study treatment; • Efficacy evaluation shows progression of disease (evaluated by investigator), unless the subject meets the criteria for treatment beyond progression; • Pregnancy in female subject occurs during the study; • Subject can still not tolerate the toxicity after dose adjustment, or adverse event, laboratory examination abnormality or co-morbidities occur, and continued participation in the study is judged by investigators as violating the subject's optimal benefit; • Overall deterioration of health status, inability to continue participation in the trial; • Other reasons for inability to continue study treatment, as considered by investigators. |
| Criteria for Withdrawal From the Study | 
The reasons for withdrawal from the study may include:
 
 • Withdrawal of the informed consent on participation in the study, and refusal of further follow-up; • Other conditions that necessitate the withdrawal from the study, as considered by investigators, for example, loss of the ability to express his/her wishes freely due to imprisonment or detachment; • Lost to follow-up; • Death; • Termination of study by the sponsor or health authority. |
| Criteria for Study Termination | 
The criteria for termination of this study include but not limited to the following:
 
 • Discovery of unexpected, significant or unacceptable risk; • Low compliance with study requirements. |
| Safety Evaluation | 
The severity of adverse events will be judged in accordance with CTCAE v4.03. Adverse event record forms should be filled out during the trial, including the occurrence time, severity, relationship with the study drug, duration, measures taken and outcome of the adverse event.
 |
| Efficacy | 
To evaluate OS, subjects after study treatment termination will
 |

| | |
|---|--|
| 
Evaluation
 | 
have their survival status collected through site visits or telephone follow-up on a regular basis until death. Subject who died during the trial, their actual time of death will be recorded.
 
6 months PFR: defined as the progression free survival rate at 6 months after enrollment. Evaluations of PFR well as PFS, ORR, DCR and DoR will be performed based on RECIST v1.1 and iRECIST: The radiological evaluation will be performed once every 8 weeks; and can be performed in a real-time manner if new lesion is suspected; the efficacy must be confirmed in 4 weeks for the subjects who are firstly evaluated as PR/CR. The progression of disease that is suspected as pseudoprogression needs to be confirmed in subsequent radiological examinations, the time of the radiological examination for confirmation is at least 4 weeks after progression of disease is found or at the next scheduled time point (not exceeding 12 weeks), and prior to termination of study treatment. The patients who meet RECIST v1.1 criteria for progression will continue to receive tumor assessment until progression of disease (meeting the definition of iRECIST) or termination of study treatment, whichever occurs later. Once clinical progression occurs at any time, physical examination and immediate confirmation by imaging rather than waiting for the next scheduled imaging examination need to be done for the subject.
 |
| 
Sample Size Determination
 | 
The trial was designed to discard a PFS at 6 month of 37% (null hypothesis) aiming to reach a PFS at 6 month of 60% or higher (alternative hypothesis). Using Simon's optimum two-stage design and setting α-error at 0.05 and β-error at 0.10, the presence of at least six successes in the 12 patients enrolled in the first stage allowed the trial to proceed to the second stage in which 31 more patients were needed to be enrolled for the minimum total of 43 patients.
 |
| 
Data Analysis / Statistical Methods
 | 
Efficacy Analyses
 
The two primary endpoints for the study are PFR (base on RECIST v1.1).
 
PFR will be evaluated by stratified Log-rank test and the corresponding 95% confidence interval (CI) will be estimated in a stratified Cox proportional hazard model. The PFS and OS curves will be estimated using the Kaplan-Meier (KM) product-limit method. A 95% CI for median PFS and OS will be estimated by Brookmeyer-Crowley method.
 
ORR and DCR will be assessed according to RECIST v1.1. ORR and DCR according to RECIST v1.1 will be performed using stratified Cochran-Mantel-Haenszel (CMH) test at 0.025 one-sided. Difference in proportions for ORR and DCR, and their 95% CI using normal approximation will be provided.
 |

| | |
|---------------------|---|
| | 
Overall response rates and their corresponding 95% exact CIs will be calculated by Clopper-Pearson method.
 
The other time-to-event endpoints will be estimated using the Kaplan-Meier (KM) product-limit method, unless specified. A 95% CI for median survival time will be estimated by Brookmeyer-Crowley method, if necessary.
 
For other binary variables, stratified CMH test will be used and two-sided 95% CI for treatment difference will be calculated using normal approximation.
 
Safety Analyses
 
Safety data including Adverse events (AEs) and laboratory results will be summarized descriptively using summary statistics.
 
Other Analyses:
 
Exploratory endpoints including average scores and its change from baseline obtained from EORTC QLQ-C30 will be summarized descriptively using summary statistics.
 |
| End of Study | 
For this study, end of study is defined as the date of the Last Patient's Last Visit (LPLV).
 |
| Study Period | 
Estimated enrollment for first subject in: Jan 2018
 
Estimated enrollment for last subject in: Jan 2019
 
Estimated end of study: Jun 2019
 |

SCHEDULE OF ACTIVITIES

| Item/evaluation time | Screening period ^a | Treatment period | | Follow-up period | |
|---|-------------------------------|------------------|------------------------|-------------------------------------|------------------------|
| | | Treatment period | End-of treatment visit | Every 8 weeks in 36 weeks until PDb | End-of treatment visit |
| | | D1 | D15 | D8 | D29 |
| Signature of informed consent form | X | | | | |
| Determination of inclusion / exclusion criteria | X | | | | |
| Demographics | X | | X | | X |
| Physical examination ^d | X | X | X | | X |
| Vital signs ^d | X | X | X | | X |
| Body surface area (BSA) ^e | | X | | | X |
| ECOG PS | X | X | X | | X |
| EKG | X ^f | | X | | X |
| AE ^d | X | X | X | X | X |
| Concomitant medication | X | X | X | X | X |
| Quality of life ^l | X | | X | | X |
| Laboratory examination | | | | | |

SCHEDULE OF ACTIVITIES

| Item/evaluation time | Screening period ^a | Treatment period | Follow-up period | |
|--|-------------------------------|----------------------|---|--|
| | | Treatment period | Every 8 weeks in 36 weeks until PD ^b | End-of treatment visit |
| Hematology | X | D1 X ^h | D8 | D15 D22 D29 |
| Liver and kidney function, blood electrolyte | X | X ^h | | X X X |
| Urinary pregnancy test ^l | X | | | |
| Study treatment | | | | |
| Apatinib Mesylate Tablets 500mg | | X ^m | X ^m | X ^m X ^m X ^m |
| SHR-1210 200mg Q2W (for 36 weeks) | | X | | X |
| Curative effect | | | | |
| Tumor imaging evaluation | X ^b | | | X ^b X ^b X ^b |
| AE | X ^k | | | X ^k X ^k X ^k |

BSA = body surface area; ECG = electrocardiogram; PD = disease progression;

- The informed consent should be signed within 2 weeks before the medication. Screening evaluation should be completed within 2 weeks before medication.
- The disease was assessed using the same radioimaging techniques (CT scan or MRI), every 8 weeks during the treatment period and every 12 weeks during the follow-up period until the disease progressed, the subjects began follow-up anti-cancer treatment, the end of the study or the subjects died. Disease assessment should include enhanced CT or MRI of the primary tumor site, chest plain CT, ECT whole body bone imaging or whole body PET/CT examination.

- c. Subjects will continue to receive research medication until the disease progresses or unacceptable toxicity occurs. End-of-treatment visits should be conducted within 4 weeks of the last drug administration and adverse events within 4 weeks of the last drug administration should be recorded.
- d. The abnormal changes of clinically significant physical examination results (including vital signs and ECOG physical condition score) should be recorded as adverse events, and PD should not be reported as adverse events.
- e. does not need to recalculate BSA every cycle unless the research center guidelines require or subjects to gain or lose more than 10% of their original weight. For obese subjects (BMI > 30), BSA should be calculated using ideal body weight throughout the study period.
- f. To record adverse events within 4 weeks after the last administration of the drug. Drug-related grade 3 or 4 toxicity was monitored until it was reduced to grade 2 or below, or at least 24 weeks after the last drug administration, whichever was earlier. Liver or cardiac toxicity of grade 2 to 4 was monitored until it dropped to grade 1 or below, or at least 24 weeks after the last administration of the drug, whichever was earlier.
- g. Records only the date when new cancer treatments are initiated.
- h. Laboratory results must be obtained within 48 hours before administration.
- i. applies only to women of childbearing age who have sex.
- j. Survival status should be followed up at least every 12 weeks within 2 years after the last administration of the drug, and then every 24 weeks until the end of the clinical study.
- k. The formula of creatinine clearance was: $\text{Cr} = (140 - \text{age}) * \text{body weight}(\text{kg}) / [72 * \text{Scr}(\text{mg/dl})]$ or $\text{Cr} = [(140 - \text{age}) * \text{body weight}(\text{kg})] / [0.818 * \text{Scr}(\text{umol/L})]$. Women were calculated by the result *0.85

ABBREVIATIONS

| Abbreviations | Definition |
|------------------|---|
| AE | adverse event |
| ADA | antidrug antibody |
| ALP | alkaline phosphatase |
| ALT | alanine aminotransferase |
| AST | aspartate aminotransferase |
| AUC | area under the concentration time curve |
| BID | twice daily |
| BOR | best overall response |
| BUN | blood urea nitrogen |
| CK | creatinine kinase |
| C _{max} | maximum concentration |
| Cr | creatinine |
| CT | computed tomography |
| CTLA4 | cytotoxic T lymphocyte antigen 4 |
| D | Day |
| DCR | disease control rate |
| DNA | deoxyribonucleic acid |
| DoR | duration of response |
| eCRF | electronic case report form |
| ECOG-PS | Eastern Cooperative Oncology Group- Performance Status |
| EDC | electronic data capture |
| EORTC | European Organization for the Research and Treatment of Cancer |
| FAS | full analysis set |
| G-CSF | granulocyte colony-stimulating factor |
| GCP | Good Clinical Practice |
| GGT | γ-glutamyl transferase |
| GHS | general health status |
| h | hour |
| HBsAg | Hepatitis B surface antigen |
| HBV | Hepatitis B virus |
| HCC | hepatocellular carcinoma |
| HCG | human chorionic gonadotropin |
| HCV | Hepatitis C virus |
| HDL-C | high-density lipoproteincholesterol |
| HIV | human immunodeficiency virus |
| ICC | intrahepatic cholangiocarcinoma |
| ICH | International Council for Harmonisation |
| DMC | Data Monitoring Committee |
| iRECIST | immune RECIST |
| INN | international nonproprietary name (for pharmaceutical substances) |
| INR | international normalized ratio |
| LEU | leukocytes in urine |
| LVEF | left ventricular ejection fraction |

| Abbreviations | Definition |
|-----------------|---|
| IU | international unit |
| LDH | lactate dehydrogenase |
| LSLV | last subject last visit |
| LYMPH | lymphocyte |
| MFD | maximum feasible dose |
| MRI | magnetic resonance imaging |
| MTD | maximum tolerated dose |
| NCI-CTCAE v4.03 | National Cancer Institute - Common Terminology Criteria for Adverse Events Version 4.03 |
| NMPA | National Medical Products Administration |
| ORR | objective response rate |
| OS | overall survival |
| PD | progressive disease |
| PD-1 | programmed death-1 |
| PFS | progression free survival |
| PRO | patient reported outcome |
| PT | prothrombin time |
| QLQ-C30 | Quality of Life Questionnaire-Core 30 |
| RECIST v1.1 | Response Evaluation Criteria in Solid Tumors |
| RO | receptor occupancy |
| SAE | serious adverse event |
| SIE | AE of special interest |
| SS | safety set |
| TBIL | total bilirubin |
| TTD | time to deterioration |
| TTP | time to progression |
| VAS | visual analogue scale |
| WOCBP | women of childbearing potential |

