3. STUDY DESIGN

3.1. Overall Design

This is a Single-arm, Open label, Prospective, Single-center phase II trial to evaluate the efficacy and safety of PD-1 antibody SHR-1210 plus apatinib mesylate as seconde/third-line therapy in patients with advanced osteosarcoma.

The study will be conducted in subjects with incurable, locally advanced or metastatic osteosarcoma who had progressed upon first-line/second-line chemotherapy including high-dose methotrexate, doxorubicin, cisplatin with or without ifosfamide. Primary efficacy endpoints include both CBR and PFS evaluated by the BIRC based on RECIST v1.1, and approximately 43 subjects will be enrolled. Eligible subjects will receive SHR-1210 combined with apatinib mesylate (experimental arm).

Subjects will receive study treatment after being informed of all pertinent aspects of the study, signing the informed consent form and passing the screening for eligibility. Experimental arm: SHR-1210, 200 mg, via intravenous infusion, once every two weeks (Q2W) + apatinib mesylate 500 mg, p.o., once per day (QD), continuously, 4 weeks (28 days) per cycle of therapy, until meeting the criteria for study treatment termination specified in the protocol. Subjects will continue to receive safety and survival follow-up after end of treatment. Subjects who discontinue treatment for reasons other than progression of disease will continue to receive regular radiological evaluation follow-up after end of treatment.

The subject will continue to receive study treatment until intolerable toxicity occurs, or until lack of clinical benefits as determined by investigator after comprehensive evaluation of radiological and laboratory examination data as well as the subject's

clinical condition (e.g., tumor symptomatic exacerbation), or until the subject voluntarily withdraws from study treatment, whichever comes first.

Following disease progression in accordance with RECIST v1.1 (evaluated by investigator), subjects may continue treatment with SHR-1210 monotherapy or in combination with apatinib, if they can still clinically benefit from and tolerate study treatment as determined by investigator (see Section 6.6 for treatment criteria after disease progression).

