10.1. Sample Size Determination

According to our previous phase II trial of single agent of apatinib on advanced osteosarcoma, the 4-m PFS rate was 56.76% (95% CI 39.43%–70.84%) and the 6-m PFS rate was 36.77% (95% CI 21.48%–52.16%). 9/37 (24.32%) patients was progression free at 6 months. Median PFS and OS were 4.44 (95% CI 3.12–7.08) and 8.77 (95% CI 6.73–16.70) months, respectively. This trial was designed to discard a PFS at 6 month of 37% (null hypothesis) aiming to reach a PFS at 6 month of 60% or higher (alternative hypothesis). Using Simon’s optimum two-stage design and setting α -error at 0.05 and β -error at 0.10, the presence of at least six successes in the 12 patients enrolled in the first stage allowed the trial to proceed to the second stage in which 31 more patients were needed to be enrolled for the minimum total of 43 patients. Power and sample calculations were performed using EAST® 6.4.1. software package.

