10.3. Analysis Populations

- **Full Analysis Set (FAS):** In line with the Intention-to-Treat (ITT) principle, this population will include all randomized subjects who receive at least 1 dose of study treatment. Subjects will be included in the experimental arm to which they are randomized.
- **Safety Analysis Set (SS):** This population will include all treated subjects who receive at least 1 dose of study treatment. For most subjects, this will be the experimental arm to which they are randomized. For subjects who take incorrect study treatment for the entire treatment period, safety data will be analyzed based on the treatment they actually receive.
- **Anti-drug Antibody (ADA) Analysis Set:** This population will include all subjects who receive SHR-1210 in combination with apatinib and had at least 1 ADA measurement.

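### The synopsis sizes the primary 6-month PFR on about 38 evaluable subjects and the body on 43 enrolled, and no denominator is fixed for the two-stage count

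*Protocol*

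**What the plan says.** The Study Design row of the synopsis states: "Primary efficacy endpoint is 6 months PFR based on RECIST v1.1, and approximately 38 subjects who could be evaluated will be enrolled". It does not say what makes a subject evaluable.

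The rest of the protocol uses another number. The synopsis sample-size row and Sections 10.1 and 10.4.5 describe a Simon two-stage design with 12 patients, then 31 more, for a total of 43. Section 3.1 says "approximately 43 subjects will be enrolled". The stage-1 rule is worded on enrolled patients: "the presence of at least six successes in the 12 patients enrolled in the first stage allowed the trial to proceed to the second stage". No final cut-off is given.

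Section 10.3 defines no evaluable set. Of its full analysis set (FAS) it says "this population will include all randomized subjects who receive at least 1 dose of study treatment", in line with intention to treat. Section 10.4.5 places the testing of PFS and OS in the FAS, by a log-rank test stratified on randomisation factors. Section 7.1 counts progression or death as the PFS event.

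**The concern.** The primary decision is a count of successes against a threshold, so the denominator matters as much as the numerator. The protocol offers two totals, one of them qualified by an undefined word.

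The analysis-set text does not settle the matter for that count. Nobody is randomised in this single-arm trial, yet the FAS is defined on randomised subjects. The sentence that invokes the FAS governs a stratified log-rank test, which needs a comparator and strata that the trial does not have. The Simon count itself is assigned to no analysis set.

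The patients at issue are those without a usable scan. Appendix 1 (RECIST v1.1, 2.6) calls a time point with no imaging not evaluable. Section 6.6.2 reports a patient who stops for general deterioration without objective progression as symptomatic deterioration, not as progression. Section 7.1 covers such a patient on death, but not before. Appendix 1 (2.7) also says that the conditions for early progression, early death and inevaluability should be described in each protocol, and this protocol does not describe them. If such patients left the denominator and were mostly treatment failures, the observed rate would rise with no change in efficacy.

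**Working it through.** **Inputs.** From Section 10.1: null rate 0.37, alternative 0.60, "setting α -error at 0.05 and β -error at 0.10", 12 patients in stage 1, at least 6 successes to continue, total 43. From the synopsis: 38 evaluable. Assumed, because the protocol states none: the final cut-off is the smallest that keeps the exact type I error at or below 0.05.

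**Formula.** With stage-1 size 12, total n, final cut-off c and success probability p,

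P(pass) = Σ (x = 6 to 12) P(X1 = x) · P(X2 ≥ c − x), where X1 ~ Bin(12, p) and X2 ~ Bin(n − 12, p).

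**Step 1: the plan's own design.**
- n = 43, c = 21: type I error 0.0499, power 0.819.
- n = 38, c = 19: type I error 0.0489, power 0.805.

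The stated 90% power does not reproduce with 6 of 12 at stage 1. The optimum design for β = 0.10 is 20 patients, then 44 in total. The rule of 6/12 with 19/38 is exactly the Simon optimum for β = 0.20, and 38/(1 − 0.10) = 42.2, which rounds up to 43. So 38 may be a calculated size and 43 the same size inflated by about 10%. This is an inference, and the power question is a separate point.

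**Step 2: selective loss.** Let the true all-treated rate be 0.37, and let d of every 43 patients be left out, all of them failures. The rate among those counted is 0.37 × 43/(43 − d). For d = 5 this is 15.91/38 = 0.419. Hold the rule at 6/12 and 19/38:

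| Failures left out per 43 | Rate among those counted | Type I error | Ratio to 0.0489 |
|---|---|---|---|
| 0 | 0.370 | 0.0489 | 1.0 |
| 1 | 0.379 | 0.0609 | 1.2 |
| 2 | 0.388 | 0.0757 | 1.5 |
| 3 | 0.398 | 0.0938 | 1.9 |
| 4 | 0.408 | 0.1158 | 2.4 |
| 5 | 0.419 | 0.1424 | 2.9 |

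**Step 3: softer assumptions for a loss of five.**
- Stage 1 intact, all five failures lost in stage 2. The success count is unchanged, so passing means at least 6 of 12 and at least 19 successes among all 43: 0.112.
- Some of those left out would have been progression-free, with probability q. The rate is (0.37 − q × 5/43)/(1 − 5/43). For q = 0.1 it is 0.4055, giving 0.110. For q = 0.2 it is 0.3924, giving 0.083.
- Loss unrelated to outcome: the rate stays at 0.37 and the error at 0.0489.

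**The case against.** The best defence is that the body already answers the question. The FAS takes in everyone with at least one dose, Section 10.4.5 tests PFS in the FAS, death is an event, and no evaluable set exists. The synopsis sentence can be read as a recruitment target, since it says how many will be enrolled and does not license exclusions. Section 10.4.5 leaves censoring rules to the SAP, which is not at hand.

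Much of this stands. A reader might infer that the plan is to analyse evaluable patients only, or that it expects to drop 5 of 43. The documents support neither: 38 and 43 are never linked, and the absence of an evaluable set points the other way. A reader might also argue that the 37% null counts every patient in the earlier apatinib trial, because Section 10.1 reports "9/37 (24.32%) patients was progression free at 6 months". That does not hold, since 9/37 is 24.32%. The null follows the separate 36.77% PFS estimate, so the crude count says nothing about comparability of denominators.

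What does not stand is that the body text closes the gap. The FAS sentence belongs to a test that one arm cannot run, and it is not applied to the Simon count. A conflict between two totals in the protocol is also not a detail left to the SAP. Section 10 itself requires critical revisions to the definition or analysis of the primary endpoints to go into a protocol amendment.

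**Conclusion.** The point holds as an inconsistency on the primary decision rule: two totals, an undefined word, and no denominator named for the stage-1 and final counts. It does not show that the 5% error is already lost. It shows how little slack there is: leaving out one failure per 43 takes the error from 4.9% to 6.1%.

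A reader might infer that the false-positive rate roughly triples. The 14.2% is an upper case. It needs five of 43 left out, all of them failures, spread over both stages, and the assumed cut-off of 19 of 38. With fewer losses, or some non-failures among them, the figure lies between 4.9% and 14.2%. With loss unrelated to outcome there is no inflation. The documents give no rate or cause of inevaluability, so they do not place the trial within this range. Severity: should fix.

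**What to change.** Reconcile 38 with 43, and say how they relate if both are meant to stay. In the synopsis and Sections 10.1 and 10.4.5, state that the stage-1 count (first 12 treated) and the final 6-month PFR both use all patients who receive at least one dose. Remove no treated patient for lack of a post-baseline scan, and count anyone not shown to be progression-free at 6 months as not a success. Report the evaluable-only rate as a sensitivity analysis that cannot decide success.

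The cost is wording only, with no added patients or procedures. The reported rate may be a few points lower. For illustration, 16 successes give 16/38 = 42.1% among evaluable patients and 16/43 = 37.2% among all treated. Patients lost for reasons unrelated to outcome would also count against the regimen, which is conservative.
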